### **7.9.4 WPAI:GH**

Unless otherwise specified, the analysis of WPAI:GH will be performed in all randomized subjects who have an assessment at baseline and at least one or more post-baseline assessments. The following descriptive analyses will be conducted:

- WPAI:GH questionnaire completion rate, defined as the proportion of questionnaires actually received out of the expected number (i.e., number of subjects on treatment or in follow up), will be calculated and summarized for each assessment time point by treatment group.
- Employment status (Q1, Yes/No) will be summarized at each assessment time point using
- frequency counts and percentages.
- Hours actually worked during the past 7 days (Q4) will be summarized at each assessment time
- point as a categorical variable (> 0 hour/0 hour) using frequency counts and percentages
- For the four subscores, separately:
  - Absenteeism, presenteeism, work productivity loss, and activity impairment scores and postbaseline changes in scores will be summarized at each assessment time point using descriptive statistics (i.e., N, mean with SD and 95% CI, median, first and third quartiles, minimum, maximum). Absenteeism and work productivity loss scores will be summarized for participants who were employed (Q1=Yes). Presenteeism will be summarized for participants who actually worked during the past 7 days (Q4 > 0 hour). Activity impairment will be summarized for all participants. A plot summarizing the mean change from baseline will be presented.

## 8 CONVENTIONS

The following conventions may be used for imputing partial dates for analyses requiring dates:

- For missing and partial adverse event onset dates, imputation will be performed using the Adverse Event Domain Requirements Specification
- For missing and partial adverse event resolution dates, imputation will be performed as follows (these conventions may change):
  - If only the day of the month is missing, the last day of the month will be used to replace the missing day. If the imputed date is after the death date or the last known alive date, then the latest known alive date or death date is considered as the resolution date.
  - If the day and month are missing or a date is completely missing, it will be considered as missing.
- Missing and partial non-study medication domain dates will be imputed using the derivation algorithm described in 4.1.3 of BMS Non-Study Medication Domain Requirements Specification.
- Missing and partial radiotherapy and surgery dates will be imputed using algorithm described in [APPENDIX 2](#).
- For death dates, the following conventions will be used for imputing partial dates:
  - If only the day of the month is missing, the 1st of the month will be used to replace the missing day. The imputed date will be compared to the last known alive date and the maximum will be considered as the death date.
  - If the month or the year is missing, the death date will be imputed as the last known alive date.
  - If the date is completely missing but the reason for death is present, the death date will be imputed as the last known date alive.
- For date of progression after start of study therapy, the following conventions will be used for imputing partial dates:
  - If only the day of the month is missing, the 1st of the month will be used to replace the missing day. In case of the date of death is present and complete, the imputed progression date will be compared to the date of death. The minimum of the imputed progression date and date of death will be considered as the date of progression.
  - If the day and month are missing or a date is completely missing, it will be considered as missing.
- For date of progression to prior therapies, the following conventions will be used for imputing partial dates:
  - If only the day of the month is missing, the 1st of the month will be used to replace the missing day.
  - If the day and month are missing or a date is completely missing, it will be considered as missing.
- For other partial/missing dates, the following conventions were used:

- If only the day of the month is missing, the 15th of the month will be used to replace the missing day.
- If both the day and the month are missing, “July 1” will be used to replace the missing information.
- If a date is completely missing, it will be considered as missing.

The following conversion factors will be used to convert days to months or years: 1 month = 30.4375 days and 1 year = 365.25 days.

Duration (e.g., time-to onset, time-to resolution) will be calculated as follows:

$$\text{Duration} = (\text{Last date} - \text{first date} + 1)$$

Last known alive date will be defined based on all appropriate dates collected on the CRF.

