### **7.6.9 Time-to Resolution of Select AE**

Time to resolution of the following specific events will be summarized separately for each category/subcategory.

- Time-to resolution of drug-related select AE (any grade, grade 3-5) by treatment group
- Time-to resolution of drug-related select AE (any grade, grade 3-5) where immune modulating medication was initiated, by treatment group

Time-to resolution analyses are restricted to treated subjects who experienced the specific events. Time-to resolution where immune modulating medication was initiated analyses are restricted to treated subjects who experienced the specific events and who received immune modulating medication during the longest select AE.

The following summary statistics will be reported: percentage of subjects with resolution of the longest select AE, median time-to resolution along with 95% CI (derived from Kaplan-Meier estimation) and ranges.

See time-to resolution definition subsection of Appendix 1 for additional details. The analyses will be conducted using the 30-day safety window.

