### **Time-to resolution definition**

In order to derive the time-to resolution, overlapping or contiguous AEs within a specific category or subcategory will be collapsed into what will be termed “clustered” AEs. For example, if a subject (without pre-treatment AE) experienced an AE from 1st to 5th January, another AE (with different PT but within same category) from 6th to 11th January and same AE from 10th to 12th January, these will be collapsed into one clustered AE from 1st to 12th January. [Table 1](#) is summarizing key derivation steps for each type of clustered AEs.

Time-to resolution of AE (any grade) for a specific category is defined as the longest time from onset to complete resolution or improvement to the grade at baseline among all clustered AEs in this category experienced by the subject. Events which worsened into grade 5 events (death) or have a resolution date equal to the date of death are considered unresolved. If a clustered AE is considered as unresolved, the resolution date will be censored to the last known alive date. Improvement to the grade at baseline implies that all different events in the clustered adverse event should at least have improved to the corresponding (i.e., with same preferred term) baseline grade. This measure is defined only for subjects who experienced at least one AE in the specific category.

The time-to resolution of AE (grade 3-5) for a specific category is defined similarly with an onset date corresponding to a grade 3-5 AE.

Time-to resolution of drug-related AE (any grade or grade 3-5) for a specific category is defined similarly but restricted to drug-related AE.

The time-to resolution of AE (any grade or grade 3-5, drug-related or all) where immune modulating medication was initiated is defined similarly. For data presentation not restricted to IMAE, the additional condition that the subject started an immune modulating medication during the longest AE resolution period will be applied.

Time-to resolution for a specific subcategory is defined similarly but restricted to event of this subcategory.

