## **APPENDIX 2 MISSING AND PARTIAL RADIOTHERAPY AND SURGERY DATES IMPUTATION ALGORITHMS**

### **Procedures – Imputation Rules.**

If reported procedure start date is a full valid date then set start date equal to the date part of procedure start date.

In case of partial date use imputation rules described below:

- If only day is missing then
  - If month and year of procedure match month and year of first dose date then impute as date of first dose;
  - If month and year of procedure don't match month and year of first dose date then impute as first day of that month and year.
- If both day and month are missing, then impute as maximum between 01JAN of the year and date of the first dose;
- If date is completely missing or invalid then leave missing.

Note: Imputation is not applicable to data where start date is not collected (for example "PRIOR RADIOTHERAPY" CRF). Set start date to missing in this case.

If reported end date is a full valid date then set end date equal to the date part of the reported end date.

In case of partial date use imputation rules described below:

- If reported end date is partial then set end date equal to the last possible reported end date based on the partial entered reported end date.
- If reported end date is missing, continuing, unknown or invalid then set end date equal to the most recent database extraction date.

If end date was imputed then compare end date to the death date or last known alive date if subject is not dead. If posterior then end date should be imputed to death date (or last known alive date if subject not dead).

Note: Imputation of partial dates only applies to data entered on "RADIOTHERAPY" CRF page. For other CRF pages in case of partial dates set end date to missing.

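### A day-missing AE resolution in the month of death is imputed to the death date, and Appendix 1 then counts it as unresolved in the time-to-resolution summaries

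*SAP*

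**What the plan says.** SAP Section 8 covers partial AE resolution dates: "If only the day of the month is missing, the last day of the month will be used to replace the missing day". A limit follows for a filled-in date that falls later than death or last contact: "then the latest known alive date or death date is considered as the resolution date". The section notes that these resolution-date conventions are open to change.

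SAP Appendix 1, in its time-to-resolution definition, states: "Events which worsened into grade 5 events (death) or have a resolution date equal to the date of death are considered unresolved". It adds: "If a clustered AE is considered as unresolved, the resolution date will be censored to the last known alive date". AEs of one category that overlap or follow on directly are merged into clusters, and the longest time to resolution among a participant's clusters is the one analysed.

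Section 7.6.9 reports, for drug-related select AEs, the "percentage of subjects with resolution of the longest select AE" with a Kaplan-Meier median, its confidence interval and ranges. Section 7.6.10 reports time to resolution for immune-mediated AEs (IMAEs), with by-subject listings for the longest cluster.

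Neither Section 8 nor Appendix 1 separates an imputed resolution date from a recorded one.

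**The concern.** The two rules serve different purposes. Section 8 gives a usable date to an AE for which the site entered a resolution month. Appendix 1 lists a resolution on the death date alongside AEs that became fatal, which suggests it is aimed at AEs still open at death, although the SAP does not say so. Applied in sequence, Section 8 creates the very date that Appendix 1 reads as non-resolution, so a programmer following the text exactly would reverse the status of an AE recorded as resolved.

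At stake are descriptive safety outputs: percentage resolved, the Kaplan-Meier estimate, and resolution listings that could contradict the site's record. The affected records occur only in participants who die, so the error is tied to mortality.

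**Working it through.** No stated figure needs reproducing, so the check applies the two rules in order.

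**Step 1, the imputed date.** Let D be the day of death and L the last day of that month. L is never before D. If L > D, the limit moves the date back to D. If L = D, it is already there. Either way, a resolution in the month of death with the day missing is dated D.

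**Step 2, the status.** Appendix 1 takes a resolution date of D as unresolved and censors at the last known alive date, A.

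**Step 3, how to read the limit.** Its wording names two dates without saying which applies. All calendar combinations for 2019 to 2021 were enumerated, with death from day 2 onward, actual resolution on a day r before death, and A anywhere from r to D. A month of L days gives C(L+2, 3) − L combinations:
- 31 days: 5,456 − 31 = 5,425, for 21 months: 113,925
- 30 days: 4,960 − 30 = 4,930, for 12 months: 59,160
- February: 2 × (4,060 − 28) + (4,495 − 29) = 12,530
- Total: 185,615

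| Reading of the limit | Dated D, hence unresolved |
|---|---|
| Death date if the participant died | 185,615 of 185,615 (100%) |
| Later of the two dates | 185,615 of 185,615 (100%) |
| Last known alive date even after death | 16,147 of 185,615 (8.7%) |

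The third row holds only the combinations with A = D, that is L(L − 1)/2 per month: 21 × 465 + 12 × 435 + 2 × 378 + 406 = 16,147. These are shares of enumerated dates, not expected rates in the trial.

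The first reading is the natural one. Appendix 2 writes the same kind of limit for procedure end dates as "If posterior then end date should be imputed to death date (or last known alive date if subject not dead". Section 7.5.6 likewise uses the last known alive date for participants who are alive and the death date for those who died.

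**Step 4, an example with assumed dates.** Onset is 1 March, actual resolution 5 March recorded only as March, and death 20 March.
- Actual: resolved, 5 − 1 + 1 = 5 days.
- Under the SAP: 31 March is moved to 20 March, which is the death date. The AE is unresolved and censored at A, at up to 20 − 1 + 1 = 20 days.
- By contrast, a resolution recorded only as February would be dated to the end of February, before death, and would stay resolved (given contact after February).

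**Step 5, direction and size.** With n participants in a category and k resolved, one flip changes the percentage from 100k/n to 100(k − 1)/n, a fall of 100/n points. The documents give no n. For assumed values of 10, 20 and 50, the fall is 10, 5 and 2 points.

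For the Kaplan-Meier curve, the comparison is with the actual resolution day, and A is assumed not to precede that day. The flip removes one event and keeps the participant at risk until A. No factor (1 − events/at risk) gets smaller, so the proportion still unresolved is never lower and the median is the same or later.

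**The case against.** The strongest reply is that this may be deliberate caution. Appendix 1 applies to any resolution date equal to the death date, so it already overrides dates entered by the site. When the day is unknown in the month of death, unresolved is a defensible default for a safety summary. The SAP does not state the intent either way. Even so, the default depends only on whether the recorded month happens to be the month of death, which looks more like an accident of two rules than a policy.

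Several limits on scope stand:
- The rule governs time to resolution only.
- A flip has no effect unless the AE sets the end of the reported longest cluster.
- The summaries are further restricted: drug-related select AEs in a 30-day window; IMAEs in a 100-day window, either treated with immune-modulating medication or endocrine.
- The conventions are marked as changeable, and the limit is loosely worded. Under the last-known-alive reading most flips vanish, although nothing in the SAP points to that reading for participants who died.

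A reader might infer that every such AE is misclassified. The documents do not support that. The 100% is the share of dates that land on the death date. An AE that truly ended on the day of death is unresolved under Appendix 1 by design. If death fell on the 1st, that is the only possible day in the month. The enumeration left out both cases. A reader might also infer a longer median or a difference between arms. One added censoring need not move a median, and nothing in the documents shows a difference between arms.

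**Conclusion.** The conflict is real and minor. Read literally, with the limit taken as the death date for participants who died, the SAP can turn an AE recorded as resolved before death into an unresolved one. This affects percentage resolved, the Kaplan-Meier estimate and the by-subject resolution listings for select AEs and IMAEs. AE incidence, grade and onset tables are not affected.

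The direction is fixed under the assumptions in the working; the size is not known. The documents give no count of day-missing resolutions in the month of death, and it is probably small. The 291 deaths reported in SAP Section 5.2.1 as of 18-OCT-2021 are not a count of affected AEs. The 2 to 10 point range per flip rests wholly on assumed category sizes.

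**What to change.** Add one sentence to the Appendix 1 time-to-resolution definition. The rule on a resolution date equal to the death date applies only to complete, recorded resolution dates. It does not apply to a date that reaches the death date through the Section 8 imputation, unless the AE's recorded outcome is fatal or not resolved, or the death date is itself imputed. The last exception keeps the present rule where both dates are imputed and their order cannot be judged. The sentence assumes that an AE outcome is recorded, which the SAP does not describe. It would also help to state in Section 8 that the limit is the death date for participants who died and the last known alive date otherwise.

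Do not cap the imputed date at the day before death. With death on the 1st, that would contradict the recorded month, and it could turn AEs still open at death into resolved ones.

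The cost is small: no new data, and no effect on efficacy analyses or alpha. A few AEs that actually ended on the day of death, with a partial date, would count as resolved, while a fully recorded resolution on that day would not. The change corrects status only; the imputed duration still runs to the death date.

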8.2 Discontinuation from the Study

Participants who request to discontinue study treatment will remain in the study and must continue to be followed for protocol specified follow-up procedures. The only exception to this is when a participant specifically withdraws consent for any further contact with him/her or persons previously authorized by participant to provide this information.

- Participants should notify the investigator of the decision to withdraw consent from future follow-up **in writing**, whenever possible.
- The withdrawal of consent should be explained in detail in the medical records by the investigator, as to whether the withdrawal is from further treatment with study treatment only or also from study procedures and/or post treatment study follow-up, and entered on the appropriate CRF page.
- In the event that vital status (whether the participant is alive or dead) is being measured, publicly available information should be used to determine vital status only as appropriately directed in accordance with local law.
- If the participant withdraws consent for disclosure of future information, the sponsor may retain and continue to use any data collected before such a withdrawal of consent.

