## **7.6 Safety**

### **7.6.1 Deaths**

Deaths will be summarized by treatment group:

- All deaths, reasons for death

- Deaths within 30 days of last dose received, reasons for death
- Deaths within 100 days of last dose received, reasons for death

By-subject listing of deaths will be provided for the all enrolled subjects population.

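### A death recorded with a year but no month is dated to the last known alive date, even when that date falls in an earlier calendar year and so cannot be right

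*SAP*

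**What the plan says.** SAP Section 8 gives three rules for incomplete death dates.

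- **Day missing.** The first of the recorded month is inserted, and then: "The imputed date will be compared to the last known alive date and the maximum will be considered as the death date".
- **Month or year missing.** "If the month or the year is missing, the death date will be imputed as the last known alive date".
- **Whole date missing.** "If the date is completely missing but the reason for death is present, the death date will be imputed as the last known date alive".

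The last known alive date is described only in general terms: "Last known alive date will be defined based on all appropriate dates collected on the CRF". It has no link to a recorded year of death.

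The same SAP treats year-only dates differently elsewhere. For procedure start dates, Appendix 2 says: "If both day and month are missing, then impute as maximum between 01JAN of the year and date of the first dose". Later surgeries follow the same pattern. For dates with no specific rule, Section 8 inserts 1 July of the recorded year.

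The death date is used in OS (SAP 4.1.2), in PFS when death is the first event (SAP 4.1.1), and in the safety tables of SAP 7.6.1, which include "Deaths within 30 days of last dose received, reasons for death" and the matching 100-day count.

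**The concern.** The second rule covers two different situations. If the year is missing, the last known alive date is a reasonable fallback. If the year is known and only the month and day are missing, the rule discards the year and treats the death as though its date were wholly unknown. When the last known alive date lies in an earlier calendar year, the imputed date contradicts the case record.

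The error always makes the death too early. It shortens OS, the first key secondary endpoint, and shortens PFS for a subset of deaths. It can also bring a death into the 30-day or 100-day post-dose counts, where totals may be small enough for one misdated death to show.

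**Working it through.** The plan states no figure for this rule, so there is none to reproduce. The check applies the rule to dates.

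**Inputs from the documents.** The death-date rules (SAP 8), survival contact every 3 months ±14 days after Follow-Up Visit 2 (SAP 4.1.2; Protocol Table 2-3), and 1 month = 30.4375 days (SAP 8). All calendar dates below are assumed illustrations.

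**Formulas.** L is the last known alive date and Y the recorded year of death, with the month missing.

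- SAP date = L
- Earliest date consistent with the record = max(L, 1 January Y)
- Minimum error = max(L, 1 January Y) − L
- Maximum error = 31 December Y − L

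**Results for Y = 2021.**

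| L | SAP date | Earliest possible | Minimum error |
|---|---|---|---|
| 20 Dec 2020 | 20 Dec 2020 | 1 Jan 2021 | 12 days (0.39 months) |
| 15 Nov 2020 | 15 Nov 2020 | 1 Jan 2021 | 47 days (1.54 months) |
| 2 Oct 2020 | 2 Oct 2020 | 1 Jan 2021 | 91 days (2.99 months) |
| 1 Dec 2019 | 1 Dec 2019 | 1 Jan 2021 | 397 days (13.04 months) |
| 10 Mar 2021 | 10 Mar 2021 | 10 Mar 2021 | 0 |

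The first three rows fit the contact schedule: 3 × 30.4375 = 91 days, plus some visit-window slack. The fourth needs several missed contacts. In the last row, L falls in the recorded year, so the SAP date is possible and there is no contradiction.

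For L = 15 Nov 2020 the maximum error is 411 days (13.5 months), because the death could have occurred as late as 31 December 2021.

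**Comparison with the day-missing rule.** With the same L and a death recorded as January 2021, the SAP gives max(1 Jan 2021, 15 Nov 2020) = 1 Jan 2021, which agrees with the record. Losing the month as well moves the imputed death back into 2020.

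**Post-dose death counts.**

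- Last dose 10 Nov 2020, L = 15 Nov 2020: the SAP places death on day 5. The earliest possible day is 5 + 47 = 52, so the death is wrongly in the 30-day count.
- Last dose 20 Sep 2020, L = 2 Oct 2020: the SAP places death on day 12. The earliest possible day is 12 + 91 = 103, so the death is wrongly in both counts.

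Both examples need contact to have lapsed before Follow-Up Visit 1, due 30 days after the last dose.

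**Effect on the OS hazard ratio.** I simulated 700 participants and 300 deaths with the SAP's assumed medians (36.9 and 49.2 months). I assumed exponential survival and uniform accrual over 27 months, and ran 2,000 replicates. The choice of six affected deaths is mine and has no source in the documents.

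- Six random deaths moved 3 months earlier: mean change 0.000; 95th percentile of absolute change 0.001.
- Six random deaths moved 18.1 months earlier: mean change 0.000; 95th percentile 0.007.
- All six in the combination arm: mean change about 0.002 for 3 months and 0.010 for 18.1 months.

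**The case against.** The strongest reply is that this seldom happens and barely matters. Three things must coincide: year known, month missing, and last known alive date in an earlier year. The protocol works against that. Once a death is established, Section 8.3 has the site seek its date and cause, the sponsor may request extra survival checks, and SAP 5.2.1 describes a survival sweep before the lock. The rule is the same in both arms and does not alter the number of deaths, so the OS boundaries are unaffected. Primary PFS is touched only for deaths without earlier progression or subsequent therapy. All of this stands, and it limits the size of the point.

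It can also be said that the conventions are optional, since Section 8 opens with "The following conventions may be used for imputing partial dates for analyses requiring dates". That does not help: the death-date item itself says its conventions will be applied, and no alternative is offered.

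A further objection concerns timing. The PFS final analysis and OS IA1 were run on 09MAR2021 and treatment assignments were unblinded to the sponsor (SAP 2.3 and 5.2.1). A change now comes after that, and could make some OS times differ from those used at IA1. This is a fair cost, and the fix has to address it. The replacement date is also still the earliest possible one, so some early bias remains, but the date no longer contradicts the record.

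Some stronger readings are tempting and not supported:

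- *That the last known alive date usually sits near the last dose, so the early-death tables are generally inflated.* Anyone seen at Follow-Up Visit 2 (100 ±7 days) is already past 30 days, and anyone with a later survival contact is past both windows.
- *That the affected deaths are mainly those of participants lost to contact and found through public records.* Protocol 8.2 says only that "publicly available information should be used to determine vital status only as appropriately directed in accordance with local law". It does not show who has incomplete dates.
- *That the number or typical size of the errors is known.* The documents give no count, and an error of a year or more requires a run of missed contacts.

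**Conclusion.** The rule is wrong as written for one identifiable case, and nothing else in either document corrects it. When the month is missing, the year is known and the last known alive date is in an earlier year, the imputed date is impossible. The resulting time is too short by at least the gap to 1 January of the recorded year: typically up to about 3 months if survival contacts were kept, and more only if they were missed. Misplacement into the 30-day or 100-day death counts additionally requires contact to have lapsed soon after the last dose.

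The number of affected deaths is unknown and probably small. The death count and the stated OS power of about 69% are unaffected. A reader might infer that the OS comparison is compromised; the documents do not support that, and even the pessimistic illustration of six affected deaths moves the hazard ratio by about 0.01 at most on average. The reason to act is that the plan would put dates known to be false into a key secondary endpoint and the safety tables, when its own day-missing rule and Appendix 2 already show how to avoid it.

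**What to change.** Split the second death-date rule in SAP Section 8:

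- Year known, month missing: death date = the later of 1 January of the recorded year and the last known alive date.
- Year missing: death date = the last known alive date, as now.

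Apply this at the final OS analysis, whose lock SAP version 5.0 still describes as ahead. Report the number of imputed death dates by arm and by type of missingness. State whether any death date used at the PFS final analysis or OS IA1 changes under the new rule; if none does, one sentence closes the matter.

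The cost is one sentence of SAP text, one programming condition and a small table. The downside is a rule change made after the sponsor was unblinded to treatment assignment. The amendment should record that it was made without reference to OS results by arm.
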